## Vaccinations

The use of live vaccines and close contact with those who have received live vaccines should be avoided during treatment with everolimus. Examples of live vaccines are: intranasal influenza, measles, mumps, rubella, oral polio, BCG, yellow fever, varicella, and TY21a typhoid vaccines.

For further details refer to the current everolimus Investigator's Brochure.

### 6.4.3 Prohibited concomitant therapy

Treatment with systemic anticancer agents (chemotherapy, hormone therapy, targeted or biologic agents) other than everolimus is not permitted until disease progression is documented and everolimus is permanently discontinued.

### 6.4.4 Use of Bisphosphonates (or other concomitant agents)

Not applicable.

## 6.5 Patient numbering, treatment assignment or randomization

### 6.5.1 Patient numbering

Each patient is identified in the study by a Subject Number (Subject No.), that is assigned when the patient is first enrolled in the roll-over study and is retained as the primary identifier for the patient throughout his/her entire participation in the trial. The Subject No. consists of the Center Number (Center No.) (as assigned by Novartis to the investigative site) with a sequential patient number suffixed to it, so that each subject is numbered uniquely across the entire database. Upon signing the informed consent form, the patient is assigned to the next sequential Subject No. available to the investigator through the Oracle Clinical RDC interface (OCRDC).

Additionally an eCRF will be completed that identifies the patient by gender and date of birth and previous study, site/center and subject number.

### 6.5.2 Treatment assignment or randomization

All consented patients who meet all the inclusion criteria and none of the exclusion criteria are eligible to receive everolimus.

### 6.5.3 Treatment blinding

Not applicable.

## 6.6 Study drug preparation and dispensation

The investigator or responsible site personnel must instruct the patient or caregiver to take the study drugs as per protocol. Study drug(s) will be dispensed to the patient by authorized site personnel only. All everolimus dosages prescribed to the patient and all dose changes during the study must be recorded on the Everolimus Dosage Administration Record eCRF.

**Table 6-5 Preparation and dispensing**

Study treatments	Dispensing	Preparation
Everolimus	Blister packed tablets (2.5 – 10 mg) including instructions for administration will be dispensed by study personnel on an outpatient basis. Patients will be provided with an adequate supply of study treatment for self-administration at home until at least their next scheduled quarterly (12 weeks ± 1 week) study visit. If study drug is supplied by Novartis Drug Supply Management, the supply may be dispensed more frequently if required based on local practice or drug expiration date.	Not applicable

### 6.6.1 Study treatment packaging and labeling

Everolimus for the roll-over study can be provided where appropriate as local commercial material or as global open-label supply, packed and labeled under the responsibility of Novartis Drug Supply Management. Study treatment labels will be in the local language and comply with the legal requirements of each country. They will include storage conditions for the drug but no information about the patient.

If everolimus is provided and labeled in-country, the locally-approved form and packaging of everolimus will be used.

**Table 6-6 Packaging and labeling**

Study treatments	Packaging	Labeling (and dosing frequency)
Everolimus	Tablets in blisters*	As per local requirements

\* For centrally supplied medication. If everolimus is sourced and labeled in-country/locally, the locally-approved form, packaging and labeling of everolimus will be used.

## 6.6.2 Drug supply and storage

Study treatments must be received by designated personnel at the study site, handled and stored safely and properly, and kept in a secured location to which only the investigator and designated site personnel have access. Upon receipt, everolimus should be stored according to the instructions specified on the drug labels and in the Investigator's Brochure.

**Table 6-7 Supply and storage of study treatments**

Study treatments	Supply	Storage
Everolimus	Centrally or locally supplied by Novartis	Refer to study treatment label or local product information

## 6.6.3 Study drug compliance and accountability

### 6.6.3.1 Study drug compliance

Compliance will be assessed by the investigator and/or study personnel at each patient visit and information provided by the patient and/or caregiver will be captured in the Drug Accountability Form and other relevant source documents.

### 6.6.3.2 Study drug accountability

The investigator or designee must maintain an accurate record of the shipment and dispensing of study treatment in a drug accountability log. Drug accountability will be noted by the field monitor during site visits and at the completion of the study. Patients will be asked to return all unused study treatment and packaging on a regular basis, at the end of the study or at the time of study treatment discontinuation.

### 6.6.3.3 Handling of other study treatment

If the patient was receiving a combination therapy with an approved, commercially available treatment with everolimus in the parent protocol, and is eligible for the roll-over study, this combination therapy will be allowed until the patient permanently discontinues everolimus. All Sandostatin LAR® Depot dosages prescribed to the patient and all dose changes during the study must be recorded on the Sandostatin Dosage Administration Record eCRF.

Dispensation, compliance and accountability of any combination therapy administered to the patient is under the supervision and discretion of the investigator. Sandostatin LAR® Depot will be provided by Novartis or by the investigational site considering local regulations. Sandostatin LAR® Depot will be distributed in country-specific approved packaging.

#### **6.6.4 Disposal and destruction**

At study close-out, and, as appropriate during the course of the study, the investigator will return all used and unused study treatment, packaging, drug labels, and a copy of the completed drug accountability log to the Novartis monitor or to the Novartis address provided in the investigator folder at each site.

[figure not shown]
The study drug can only be destroyed once the study drug accountability check has been done by the monitor. The study drug can be destroyed at the local Novartis facility or by a third party, as appropriate.

### **7 Visit schedule and assessments**

#### **7.1 Study flow and visit schedule**

[figure not shown]
Table 7-1 lists all of the assessments and indicates with an “X”, the visits when they are performed. A visit window of  $\pm 1$  week is allowed. All data obtained from these assessments must be supported in the patient’s source documentation.

The table indicates in the “Category” column which assessments produce data to be entered in the database (D) or documented at the site level in the source documents (S).

**Table 7-1 Visit evaluation schedule**

	Category	Protocol reference section	Enrolment	Quarterly (every 12 weeks± 1 week) visits during treatment phase	End of treatment (EoT)	30 day safety follow-up post last dose of study drug/ End of Study
Visit Number			1	Visit 2, 3, 4 etc.	777	
Obtain informed consent	D	7.1.2	x			
Patient's previous study,site, and subject number	D	7.1.2.3	x			
Demography	D	7.1.2.3	x			
Relevant medical history/current medical conditions	D	7.1.2.3	x			
Inclusion/exclusion criteria	D	5.2 / 5.3	x			
Serum pregnancy testing	D	7.2.2	x		x	
Urine pregnancy testing	S/D	7.2.2		monthly		
Adverse events and Serious adverse events	D	8.1 / 8.2	x	continuous	x	x
Everolimus dosing administration	D	6.6	x	continuous		
Sandostatin LAR® Depot dosing administration (if applicable)	D	6.6	x	continuous		
Confirmation of Clinical Benefit from Study Treatment	D	6.1.5	x	continuous		
End of study treatment	D	7.1.5			x	
Study evaluation completion	D	7.1.5				x

### **7.1.1 Molecular pre-screening**

Not applicable.

### **7.1.2 Screening**

At the enrollment visit the patient will complete a written informed consent. There will be no screening period for this study. Once consented, patients will be evaluated for eligibility via the inclusion and exclusion criteria.

#### **7.1.2.1 Eligibility screening**

Not applicable.

#### **7.1.2.2 Information to be collected on screening failures**

Not applicable.

#### **7.1.2.3 Patient demographics and other baseline characteristics**

For patients that are eligible to participate in this roll-over study, the patients' gender, date of birth, previous study, site/center and subject number, and relevant medical history will be collected.

### **7.1.3 Run-in period**

Not applicable.

### **7.1.4 Treatment period**

The starting dose of everolimus on this roll-over protocol will be the same as the last dose that was given in the parent everolimus study. A 3 month supply of everolimus will be dispensed to the patient, or what is allowed according to local practice/regulations.

Patients must return to the study center on a quarterly basis (12 weeks  $\pm$  1 week) for resupply of study medication at which time drug dispensing information and adverse event information will be collected. At this time the dose of everolimus is based on the investigator's judgment. At every quarterly visit, the investigator is required to confirm that the patient continues to have clinical benefit and may continue treatment with study drug.

The study is expected to remain open for 10 years or until such time that enrolled patients no longer need treatment with everolimus or are able to obtain commercial supply according to local regulations for their medical condition.

### **7.1.5 Discontinuation of study treatment**

Patients will continue to be treated until they are no longer benefiting from everolimus treatment, develop unacceptable toxicities, withdraw consent, are non-compliant to the protocol, or the patient dies, whichever comes first.

At the time the patient discontinues study treatment, a visit should be scheduled as soon as possible, at which time the End of Treatment visit will be performed. End of Treatment

information will be completed in the eCRF giving the date and reason for stopping the study treatment (see [Section 7.1.5.1](#)).

At a minimum, all patients who discontinue study treatment, including those who refuse to return for a final visit, will be contacted for the required safety evaluation during the 30 days following the last dose of study treatment. The completion of the Study Evaluation Completion eCRF page is required any time a patient discontinues from the study and must be completed 30 days after the end of treatment.

Patients who discontinue study treatment should be considered withdrawn from the study after the final visit assessments are performed or when it is clear that the patient will not return for these assessments.

If a study withdrawal occurs, or if the patient fails to return for visits, the investigator must determine the primary reason for a patient's withdrawal from the study and record this information on the appropriate eCRF page.

A patient will reach the end of study when everolimus treatment is permanently discontinued and there will be **no** further follow-up study visits.

#### **7.1.5.1 Withdrawal of consent**

Patients may voluntarily withdraw consent to participate in the study for any reason at any time. Withdrawal of consent occurs only when a patient does not want to participate in the study any longer, and does not want any further visits or assessments, and does not want any further study related contact.

Novartis will continue to retain and use all research results that have already been collected for the study evaluation. All biological samples that have already been collected may be retained and analyzed at a later date (or as required by local regulations).

If a patient withdraws consent, the investigator should make a reasonable effort (e.g. telephone, e-mail, letter) to understand the primary reason for this decision and record this information.

Everolimus must be discontinued and no further assessments conducted.

Further attempts to contact the patient are not allowed unless safety findings require communication or follow up.

Patients may be withdrawn from the study if any of the following occur:

1. Adverse event(s).
2. Subject withdrew consent.
3. Lost to follow-up.
4. Administrative problems.
5. Death.
6. Disease progression.
7. Treatment duration completed as per protocol.
8. Protocol deviation
9. Sponsor decision

### **7.1.5.2 Replacement policy**

Not applicable.

### **7.1.6 Follow up for safety evaluations**

All patients must be followed up for safety evaluations for 30 days after the last dose of everolimus. At the end of this period, the investigator should contact the patient to inquire about any adverse events or serious adverse events observed during this period. This could be done via a phone contact. Following this there are **no** further follow-up study visits.

### **7.1.7 Lost to follow-up**

For patients whose status is unclear because they fail to appear for study visits without stating an intention to withdraw consent, the investigator should show "due diligence" by contacting the patient, family or family physician as agreed in the informed consent and by documenting in the source documents steps taken to contact the patient, e.g. dates of telephone calls, registered letters, etc. A patient should not be considered lost to follow-up until due diligence has been completed. Patients lost to follow up should be recorded as such on the appropriate Disposition CRF.

## **7.2 Assessment types**

### **7.2.1 Efficacy assessments**

At every quarterly visit, the investigator is required to confirm that the patient continues to have clinical benefit and may continue receiving study treatment.

### **7.2.2 Safety and tolerability assessments**

Safety will be monitored by collecting Adverse Events throughout the study on a continuous basis. See [Section 8](#).

Women of child-bearing potential must complete the following pregnancy tests:

- Baseline/Enrollment - serum pregnancy test done locally
- Every 4 weeks during treatment - urine pregnancy test. Can be administered at patient's home.
- End of Treatment visit - serum pregnancy test done locally

Women of child-bearing potential who administer urine pregnancy testing at home should complete a simple diary with the dates and the outcome of the urine pregnancy test while on study treatment. In case of a positive pregnancy test, the instructions in [Section 8.4](#) should be followed.

### **7.2.3 Pharmacokinetics**

Not applicable.

### **7.2.4 Biomarkers**

Not applicable.

### **7.2.5 Resource utilization**

Not applicable.

### **7.2.6 Patient reported outcomes**

Not applicable.

## **8 Safety monitoring and reporting**

### **8.1 Adverse events**

#### **8.1.1 Definitions and reporting**

An adverse event is defined as the appearance of (or worsening of any pre-existing) undesirable sign(s), symptom(s), or medical condition(s) that occur after patient's signed informed consent has been obtained.

Adverse events of special interest as noted in [Section 8.1.3](#) will be reported as serious adverse events.

Abnormal laboratory values or test results occurring after informed consent constitute adverse events only if they induce clinical signs or symptoms, are considered clinically significant, require therapy (e.g., hematologic abnormality that requires transfusion or hematological stem cell support), or require changes in study medication(s).

Any ongoing adverse events from the parent study will be captured as medical history in the roll-over database. Any AE that begins (or worsens) after signing of the informed consent for the rollover and during the 30-day (or 28-day) safety follow up period defined in the parent protocol should be reported in both clinical databases.

Adverse event monitoring should be continued for at least 30 following the last dose of study treatment. Adverse events (including lab abnormalities that constitute AEs) should be described using a diagnosis whenever possible, rather than individual underlying signs and symptoms. When a clear diagnosis cannot be identified, each sign or symptom should be reported as a separate Adverse Event.

Adverse events will be assessed according to the current version of the Common Terminology Criteria for Adverse Events (CTCAE). If CTCAE grading does not exist for an adverse event, the severity of mild, moderate, severe, and life-threatening, corresponding to Grades 1 - 4, will be used. CTCAE Grade 5 (death) will not be used in this study; rather, information about deaths will be collected on the EOT page.

The occurrence of adverse events should be sought by non-directive questioning of the patient (subject) during the screening process after signing informed consent and at each visit during the study. Adverse events also may be detected when they are volunteered by the patient (subject) during the screening process or between visits, or through physical examination, laboratory test, or other assessments. As far as possible, each adverse event should be evaluated to determine:

1. The severity grade (CTCAE Grade 1-4)
2. Its duration (Start and end dates)
3. Its relationship to the study treatment (reasonable possibility that AE is related: No, Yes)
4. Action taken with respect to study or investigational treatment (none, dose adjusted, temporarily interrupted, permanently discontinued, unknown, not applicable)
5. Whether medication or therapy was given (no concomitant medication/non-drug therapy, concomitant medication/non-drug therapy)
6. Whether it is serious, where a serious adverse event (SAE) is defined as in Section 8.2.1

If the event worsens the event should be reported a second time in the CRF noting the start date when the event worsens in toxicity. For grade 3 and 4 adverse events only, if improvement to a lower grade is determined a new entry for this event should be reported in the CRF noting the start date when the event improved from having been Grade 3 or Grade 4.

All adverse events should be treated appropriately. If a concomitant medication or non-drug therapy is given, this action should be recorded on the Adverse Event CRF.

Once an adverse event is detected, it should be followed until its resolution or until it is judged to be permanent, and assessment should be made at each visit (or more frequently, if necessary) of any changes in severity, the suspected relationship to the study treatment, the interventions required to treat it, and the outcome.

Progression of malignancy (including fatal outcomes), if documented by use of appropriate method (for example, as per RECIST criteria for solid tumors or as per Cheson's guidelines for hematological malignancies), should not be reported as a serious adverse event.

Adverse events separate from the progression of malignancy (example, deep vein thrombosis at the time of progression or hemoptysis concurrent with finding of disease progression) will be reported as per usual guidelines used for such events with proper attribution regarding relatedness to the drug.

## **8.1.2 Laboratory test abnormalities**

### **8.1.2.1 Definitions and reporting**

Laboratory abnormalities that constitute an Adverse event in their own right (are considered clinically significant, induce clinical signs or symptoms, require concomitant therapy or require changes in study treatment), should be recorded on the Adverse Events CRF. Whenever possible, a diagnosis, rather than a symptom should be provided (e.g. anemia instead of low hemoglobin). Laboratory abnormalities that meet the criteria for Adverse Events should be followed until they have returned to normal or an adequate explanation of the abnormality is found. When an abnormal laboratory or test result corresponds to a sign/symptom of an already reported adverse event, it is not necessary to separately record the lab/test result as an additional event.

Laboratory abnormalities, that do not meet the definition of an adverse event, should not be reported as adverse events. A Grade 3 or 4 event (severe) as per CTCAE does not automatically indicate a SAE unless it meets the definition of serious as defined below and/or as per investigator's discretion. A dose hold or medication for the lab abnormality may be

required by the protocol in which case the lab abnormality would still, by definition, be an adverse event and must be reported as such.

### **8.1.3 Adverse events of special interest**

Adverse events of special interest (AESI) are defined as events (serious or non-serious) which are ones of scientific and medical concern specific to the sponsor's product or program, for which ongoing monitoring and rapid communication by the investigator to the sponsor may be appropriate. Such events may require further investigation in order to characterize and understand them.

Adverse events of special interest are defined on the basis of an ongoing review of the safety data. AESIs are discussed in detail in the Investigator Brochure.

In addition to all serious adverse events reported on a continuous basis throughout the study, the investigator should use the SAE form to report the following medically significant potential risks noted in the Novartis Risk Management Plan for everolimus:

- Development toxicity
- Reproductive (teratogenicity) toxicity
- Intestinal obstruction /ileus
- Male infertility
- Pancreatitis
- Cholelithiasis
- Muscle-wasting/Muscle-loss

## **8.2 Serious adverse events**

### **8.2.1 Definitions**

Serious adverse event (SAE) is defined as one of the following:

- Is fatal or life-threatening
- Results in persistent or significant disability/incapacity
- Constitutes a congenital anomaly/birth defect
- Is medically significant, i.e., defined as an event that jeopardizes the patient or may require medical or surgical intervention to prevent one of the outcomes listed above
- Requires inpatient hospitalization or prolongation of existing hospitalization,
- Note that hospitalizations for the following reasons should not be reported as serious adverse events:
  - Routine treatment or monitoring of the studied indication, not associated with any deterioration in condition
  - Elective or pre-planned treatment for a pre-existing condition that is unrelated to the indication under study and has not worsened since signing the informed consent
  - Social reasons and respite care in the absence of any deterioration in the patient's general condition

- Note that treatment on an emergency outpatient basis that does not result in hospital admission and involves an event not fulfilling any of the definitions of a SAE given above is not a serious adverse event

### 8.2.2 Reporting

To ensure patient safety, every SAE, regardless of suspected causality, occurring after the patient has provided informed consent and until at least 30 days after the patient has stopped study treatment must be reported to Novartis within 24 hours of learning of its occurrence.

Any SAE that begins or worsens after signing of the informed consent for the roll-over and during the 30-day (or 28-day) safety follow up period defined in the parent protocol should be reported as an adverse event in both clinical databases; however, only one SAE report will be sent to Novartis.

- Any SAE that begins or worsens **during** the 30-day (or 28-day) safety follow up period specified in the parent study, should have an SAE report submitted to Novartis with the parent protocol study number.
- Any SAE that begins or worsens **after** the 30-day (or 28-day) safety follow-up period specified in the parent study, should have an SAE report submitted to Novartis with the roll-over protocol study number.

[figure not shown]
Any additional information for the SAE including complications, progression of the initial SAE, and recurrent episodes must be reported as follow-up to the original episode within 24 hours of the investigator receiving the follow-up information. An SAE occurring at a different time interval or otherwise considered completely unrelated to a previously reported one should be reported separately as a new event.

It is important to use the right SAE form with the correct protocol number for these two scenarios, to avoid confusion in SAE processing. For a patient already on the roll-over protocol but follow up information is reported for the previous SAEs in the parent protocol, it must be clearly labeled that this is for the parent protocol number.

Any SAEs experienced after the 30 day safety evaluation follow-up period should only be reported to Novartis if the investigator suspects a causal relationship to the study treatment.

Information about all SAEs is collected and recorded on the Serious Adverse Event Report Form; all applicable sections of the form must be completed in order to provide a clinically thorough report. The investigator must assess and record the relationship of each SAE to each specific study treatment (if there is more than one study treatment), complete the SAE Report Form in English, and submit the completed form within 24 hours to Novartis. Detailed instructions regarding the SAE submission process and requirements for signatures are to be found in the investigator folder provided to each site.

Follow-up information is submitted in the same way as the original SAE Report. Each re-occurrence, complication, or progression of the original event should be reported as a follow-up to that event regardless of when it occurs. The follow-up information should describe whether the event has resolved or continues, if and how it was treated, whether the blind was broken or not, and whether the patient continued or withdrew from study participation.

If the SAE is not previously documented in the Investigator's Brochure or Package Insert (new occurrence) and is thought to be related to the Novartis study treatment, an oncology Novartis Drug Safety and Epidemiology (DS&E) department associate may urgently require further information from the investigator for Health Authority reporting. Novartis may need to issue an Investigator Notification (IN), to inform all investigators involved in any study with the same drug that this SAE has been reported. Suspected Unexpected Serious Adverse Reactions (SUSARs) will be collected and reported to the competent authorities and relevant ethics committees in accordance with Directive 2001/20/EC or as per national regulatory requirements in participating countries.

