  - AEs resulting in dose adjustment or interruption regardless of study drug relationship by primary system organ class and preferred term
  - AEs requiring additional therapy and concomitant medication regardless of study drug relationship by primary system organ class and preferred term
  - AESIs regardless of study treatment relationship
    - c. by primary system organ class, preferred term and maximum CTC grade
    - d. by primary system organ class and preferred term
  - AESIs suspected to be study treatment related
    - c. by primary system organ class, preferred term and maximum CTC grade
    - d. by primary system organ class and preferred term
  - AESIs leading to study drug discontinuation regardless of study drug relationship by primary system organ class and preferred term
  - AESIs resulting in dose adjustment or interruption regardless of study drug relationship by primary system organ class and preferred term
  - AESIs requiring additional therapy and concomitant medication regardless of study drug relationship by primary system organ class and preferred term
- SAEs after protocol amendment
  - SAEs regardless of study treatment relationship by primary system organ class and preferred term
  - SAEs suspected to be study treatment relationship by primary system organ class and preferred term

For legal requirements of ClinicalTrials.gov and EudraCT, two required tables on treatment-emergent non-serious AEs with an incidence greater than 5% in clinical database, and on-treatment deaths and treatment-emergent SAEs in ARGUS safety database will be provided by

system organ class and preferred term using the safety set. The rule for the calculation of the number of occurrences is detailed in the Appendix section 5.2.

All of these tables will display the number and percent of patients that experience the given event and will display events by MedDRA. Events will be displayed alphabetically for SOC and PT. All safety data (including those from the post-treatment periods) will be listed and those collected during the post-treatment period are to be flagged. The following listings will also be generated:

- Listing of AEs leading to study drug discontinuation
- Listing of AEs leading to dose adjustment or interruption
- Listing of SAEs in ARGUS safety database
- Listing of SAEs in RDC clinical database

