## **5.2 AEs coding/grading**

AEs will be coded using the latest MedDRA version available at time of database lock while National Cancer Institute Common Terminology Criteria for Adverse Events (NCI CTCAE) version 4.03 will be used for reporting AE severity.

The CTCAE represents a comprehensive grading system for reporting the acute and late effects of cancer treatments. CTCAE grading is by definition a 5-point scale generally corresponding to mild, moderate, severe, life threatening, and death. This grading system inherently places a value on the importance of an event, although there is not necessarily proportionality among grades (a grade 2 is not necessarily twice as bad as a grade 1).

CTCAE grade 5 (death) will not be used in this study; rather, this death information will be collected on the EOT CRF page (Panel: CMP). Grading is applicable in data collected in RDC clinical database but not ARGUS safety database.

The rule for the calculation of the number of occurrences that is provided in the summary of serious and non serious adverse events required for the legal requirements of ClinicalTrials.gov and EudraCT is the following:

If for a same patient, several consecutive AEs (irrespective of study treatment causality, seriousness and severity) occurred with the same SOC and PT:

- a single occurrence will be counted if there is  $\leq 1$  day gap between the end date of the preceding AE and the start date of the consecutive AE
- more than one occurrence will be counted if there is  $> 1$  day gap between the end date of the preceding AE and the start date of the consecutive AE

For occurrence of SAE, the presence of at least one SAE / SAE suspected to be related to study treatment / non SAE has to be checked in a block e.g., among AE's in a  $\leq 1$  day gap block, if at least one SAE is occurring, then one occurrence is calculated for that SAE.

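### Protocol 8.2.2 gives conflicting rules for filing a recurrent SAE, so the ARGUS occurrence counts in the registry SAE table may be too low and inconsistent between sites

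*Protocol*

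**What the plan says.** Protocol 8.2.2 addresses a recurrent SAE in several places.

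- On additional information: "recurrent episodes must be reported as follow-up to the original episode within 24 hours of the investigator receiving the follow-up information".
- The next sentence: "An SAE occurring at a different time interval or otherwise considered completely unrelated to a previously reported one should be reported separately".
- Later, without any time limit: "Each re-occurrence, complication, or progression of the original event should be reported as a follow-up to that event regardless of when it occurs".
- On the protocol number: an SAE that starts or worsens within the parent study's 28- or 30-day safety window is reported under the parent number; one that starts or worsens after it takes the roll-over number.
- On follow-up information about earlier parent-study SAEs in a patient already in roll-over: "it must be clearly labeled that this is for the parent protocol number".

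On the analysis side, SAP 2.8.2 plans a registry table in which "on-treatment deaths and treatment-emergent SAEs in ARGUS safety database will be provided by" system organ class and preferred term. SAP 5.2 gives "The rule for the calculation of the number of occurrences that is provided in the summary of serious and non serious adverse events required" by the two registries. For the same patient, system organ class and preferred term, "more than one occurrence will be counted if there is" a gap of more than one day between the end of one event and the start of the next; a gap of at most one day gives a single occurrence.

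SAP 2.8.2 says that its AE and SAE tables show the number and percent of patients. SAP 2.1 restricts the analysis to this protocol's database and leaves out parent-study data.

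**The concern.** A site that sees the same SAE again months later can follow 8.2.2 in two opposite ways: send follow-up to the original report, or open a new event. The occurrence rule in SAP 5.2 needs a start and an end date for each episode. If a recurrence sent as follow-up is held inside the original record, the rule has no second pair of dates to work on and counts one occurrence instead of two.

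The clinical database cannot fill the gap for the whole study. SAP 2.1 reports that 32 of 34 patients were enrolled before the amendment introduced eCRF collection of AEs, that 11 had already discontinued, and that about 50% of pre-amendment SAEs are not in RDC. The manual matching in SAP 2.8.2 concerns SAEs present in both databases. The two sources also follow different record rules: Protocol 8.1.1 has a worsened event entered a second time in the CRF with its own start date, whereas 8.2.2 sends progression of an SAE to follow-up.

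A second route could reach patient counts. If every recurrence is follow-up whatever its timing, a roll-over recurrence of a parent-study SAE is follow-up to a parent-study event and would carry the parent number. The window rule gives the roll-over number to the same event if it began after the window. Under the first reading it could drop out of the SAE tables that serve the primary objective.

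**Working it through.** The documents give no SAE count or occurrence count, so there is no plan figure to reproduce. The check has three steps.

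**1. Which rule applies to a recurrence?**

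| Case | Follow-up sentences | New-event or window rule |
|---|---|---|
| Same SAE recurs later within roll-over | Follow-up to the original | New event, if the time interval is different |
| Parent-study SAE recurs after the parent window | Follow-up, so parent number | Roll-over number |

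Both columns apply in each row, and the section sets no precedence.

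**2. What does the SAP 5.2 rule count?** Assume one patient and one preferred term, with episodes on days 10–15 and 100–105. The gap is 100 − 15 = 85 days, which exceeds 1.

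| Filing and storage | Occurrences | Patients |
|---|---|---|
| New event | 2 | 1 |
| Follow-up, held as one record | 1 | 1 |
| Follow-up, both sets of dates kept | 2 | 1 |

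Episodes on days 10–15 and 16–20 (gap 1 day) count once under any filing.

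**3. How does the count respond?** Assume 10 patients with an SAE in one term, of whom r recur once after more than one day, and a share f of recurrences merged into the original record. True occurrences are 10 + r; counted occurrences are 10 + r − r × f.

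| r | True | f = 0 | f = 0.5 | f = 1 | Shortfall at f = 1 |
|---|---|---|---|---|---|
| 0 | 10 | 10 | 10 | 10 | 0 |
| 1 | 11 | 11 | 10.5 | 10 | 1/11 = 9.1% |
| 3 | 13 | 13 | 11.5 | 10 | 3/13 = 23.1% |
| 5 | 15 | 15 | 12.5 | 10 | 5/15 = 33.3% |

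Patient incidence is 10/34 = 29.4% in every row, using the 34 enrolled patients of SAP 2.1 as denominator. The size of the Safety Set, which requires a dose, is not stated.

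For the parent-number route, each patient whose only roll-over SAE went under the parent number, and was not retrieved, would lower incidence by 1/34 = 2.9 percentage points. How many such patients there are, if any, is unknown.

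**The case against.** The strongest reply has four parts.

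*The sentences can be read together.* In the new-event sentence, the words after the alternative may make a different time interval just one sign of an unrelated event, leaving true recurrences to follow-up. Section 8.2.2 also points sites to detailed submission instructions in the investigator folder, which is not among the documents. This softens the conflict but does not remove it: the sentence joins its two conditions as alternatives, and the protocol itself should settle the matter.

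*Nothing shows that dates are lost.* Section 8.2.2 says follow-up is submitted in the same way as the original report, so ARGUS may hold dates for each episode. This stands. A reader might infer that the counts will be too low. That would require a recurrence more than one day after resolution, a site filing it as follow-up, and storage without separate dates; the documents establish none of these.

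*The window rule already deals with parent-study SAEs.* It assigns the roll-over number to an SAE that begins or worsens after the window, and SAEs inside the window go to the parent study by explicit design. So one cannot say that roll-over recurrences would be filed under the parent number; only that one sentence of 8.2.2 points that way and conflicts with the window rule.

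*The scope is narrow and the trial is near reporting.* The occurrence rule serves only the registry summary, and the 2020 SAP prepares the final CSR, so new protocol wording would change little that sites have already filed. Both points stand. They move the weight of the fix to the SAP.

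**Conclusion.** The inconsistency in Protocol 8.2.2 is real, and the SAP depends on how it is resolved. The ARGUS occurrence column of the registry SAE table may be too low, and may not be comparable between sites, by an amount that cannot be estimated from the documents. The figures in the tables above illustrate how the rule behaves; they are not estimates for this trial.

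A reader might infer that the primary endpoint as a whole is biased. The documents do not support that. When a recurrence in the same preferred term within roll-over is merged, the number and percent of patients stay the same. Patient-level counts are exposed only through the parent-number route. That route requires a site to have applied the follow-up sentence over the window rule, and the ARGUS extraction to have left the case out. How ARGUS cases are selected by protocol number is not described.

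**What to change.** **Protocol 8.2.2.** Reconcile the sentences. A recurrence that starts after the earlier episode has ended is reported as a separate event with its own onset and end dates, under the protocol number that the existing window rule assigns. Follow-up is kept for the same ongoing episode.

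**SAP 5.2.** State that ARGUS occurrences are derived from episode-level onset and end dates found in initial and follow-up reports, before the one-day gap rule is applied.

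**SAP 2.1 and 2.8.2.** Check follow-ups labelled with the parent number for episodes that began after the parent safety window. Include each such episode once, so that nothing is double-counted, and record this as a clarification of the exclusion of parent-study data, since these episodes arose during roll-over.

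The cost is wording in both documents and a manual read of the SAE follow-up reports for at most 34 enrolled patients, which can be added to the ARGUS/RDC matching that the SAP already describes. No new data collection is needed.
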